#### 7.4.2.2 Random effects crossover model including the treatment by baseline interaction MMRM2

This was also a predefined secondary analysis of the primary endpoint, on all patients in the FAS. It assumes that any treatment effect is linearly dependent upon randomisation baseline (visit 8) GFR. This will be done using the analysis model and assumptions described in [Section 7.4.2.1](#), with an additional term for the treatment-by-baseline GFR interaction. For ease of reference, it will be referred to as MMRM2.

The gradient of the treatment effect with respect to randomisation baseline GFR will be estimated, along with its 95% confidence interval and nominal p-value. Estimates for the treatment effects and their 95% CIs will be provided for a range of selected randomisation baseline GFR values (100, 115 and 130 mL/min/1.73m^2).

The same set of limited model diagnostics as in [Section 7.4.2.1.1](#) will be produced.

#### 7.4.2.3 Random effects crossover model on the natural logarithmic scale MMRM3

The primary analysis as described in [Section 7.4.2.1](#), will be repeated on all patients in the FAS with the modification that all GFR measurements (endpoint and randomisation baseline values) will be replaced by their natural logarithms (loge). Estimates from this model will be back-transformed and the estimate of the treatment effect reported as the ratio of geometric means for GFR (empagliflozin/placebo), together with its 95% CI and nominal p-value. A value of less than 1 for the ratio of geometric means therefore represents a lower mean GFR on empagliflozin compared to placebo.

For ease of reference, this will be referred to as MMRM3.

In order to examine the treatment effect, the same graphical displays (scatter plot and boxplot) as defined in [Section 7.4.2.1.3](#) will also be produced on the natural log scale.

#### 7.4.2.4 Analysis of period one ANCOVA1

An ANCOVA analysis will be conducted on the primary endpoint GFR measurements from crossover period 1 only, for all patients in the FAS. This will be referred to as ANCOVA(1).

This is to provide an estimate of the treatment effect that cannot possibly be affected by any potential carryover effect, albeit on half of the sample size compared to when both periods are included.

The data will be limited to period one data only and the statistical model will include a fixed effect for the class variable of first period treatment, and randomisation baseline GFR as a linear covariate.

In order to examine the treatment effect within period one, the same graphical displays (scatter plot and boxplot) as defined in [Section 7.4.2.1.3](#) will also be produced.

There are no planned sensitivity analyses in this early terminated study.

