### *Primary endpoint analysis*

Analyses on subgroups of GFR hyperfilterers (n=2), GFR responder (n=2) and GFR non-responder (n=0) groups are not possible because there are too few patients per group. Therefore, it is not possible to test the null hypothesis of the study.

Subsequently, no per protocol set (PPS) will be determined, however, the important protocol deviations will still be identified prior to unblinding.

The subgroup of normofilterers (n=29) is very similar to the overall set of patients in the full analysis set (FAS) (n=31) and therefore, only the overall set of patients will be analysed.

For the overall set of patients, all pre-specified analyses will be implemented, except for the pre-specified analysis using screening GFR and the screening GFR by treatment interaction. Due to the high correlation between screening GFR and baseline (pre-randomisation) GFR, it is expected that this would lead to similar findings, compared to the analysis (with interaction) using pre-randomisation GFR as baseline.

The assumptions behind the models will be investigated by way of model diagnostics and the potential period effect by graphics. Otherwise, the analyses will be as per protocol.

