### **6.6.1 Efficacy analysis**

If one of the pair of scheduled GFR measurements (or other similarly recorded data) is missing, the endpoint will be defined as the single remaining non-missing value, as specified in [Section 5.1](#). If both of the scheduled GFR measurements (or other similarly recorded data) are missing, then the endpoint is missing at that visit.

All GFR measurements available on the trial database after data cleaning activities have been completed (or other similarly recorded data) will be assumed to be technically plausible and eligible for use in the analysis, i.e. will not be set to missing programmatically in any cases.

In the event that GFR values (or other similarly recorded data) at a particular visit are outside the relevant visit window specified in [Section 6.7](#), the values will be retained in analysis datasets, but not used in any analysis.

In the event that randomisation baseline GFR is missing, or **both** double-blind treatment period GFR values are missing, such a patient will be excluded from the FAS by definition, and therefore, excluded from all analyses of GFR after 4 weeks of double-blind treatment. Since ramipril is given to lower GFR in the run-in period, under no circumstances will a missing randomisation baseline GFR be imputed by screening baseline GFR, if randomisation baseline GFR is missing after data cleaning activities have been completed.

For all continuous endpoints (including GFR after 4 weeks of double-blind treatment), any patient with only one available value will still be included in the mixed model analyses in which patient is fitted as a random effect (including the primary analysis of GFR). Missing data for one of the crossover periods is implicitly handled in this type of statistical model under the missing at random (MAR) assumption. This also means that all patients in the FAS will be included in the primary analysis of the primary endpoint. Such a patient will be excluded from other analyses in which patient is fitted as a fixed effect. If it is the first crossover period where the missing value occurs, such a patient will also be excluded from any analysis which only uses data from the first double-blind treatment period.

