##### 7.4.2.1.3 Examination of treatment effect

To investigate the treatment effect graphically, a scatter plot will be produced, displaying one treatment on the y-axis versus the other treatment on the x-axis, including a 45-degree line

and the mean of the two treatments superimposed. In addition, a boxplot showing the distribution of the GFR at week 4 by treatment will be included.

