#### 7.4.2.1.4 Examination of relationship between GFR at baseline and week 4, by treatment

To investigate the relationship between baseline GFR and GFR at week 4, by treatment, there will be a scatter plot with GFR at week 4 on the y-axis and baseline GFR on the x-axis using different symbols for each of the two treatments. In addition, GFR at week 4 will be presented by subgroups of GFR at baseline, split into three approximately equally sized groups (<107, ≥107 to <120, ≥120) using boxplots with one display per treatment group. The overall GFR (irrespective of baseline) will also be included.

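### Does the period-one ANCOVA in SAP Section 7.4.2.4 need its scatter plot cross-reference changed?

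*SAP*

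**What the plan says.** SAP Section 7.4.2.4 describes a period-one analysis of covariance of GFR in the FAS, with first-period treatment as a fixed effect and randomisation baseline GFR as a linear covariate. Its purpose is an estimate that carryover cannot affect. On the data it says "The data will be limited to period one data only". On figures it says "In order to examine the treatment effect within period one, the same graphical displays (scatter plot and boxplot) as defined in" Section 7.4.2.1.3.

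Section 7.4.2.1.3 belongs to MMRM1, which uses both periods. It defines two displays. One is a scatter plot, "displaying one treatment on the y-axis versus the other treatment on the x-axis, including a 45-degree line", with the mean of the two treatments added. The other is a boxplot of week-4 GFR by treatment.

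Section 7.4.2.1.4 defines another scatter plot, also under MMRM1: a "scatter plot with GFR at week 4 on the y-axis and baseline GFR on the x-axis using different symbols" for the two treatments.

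Section 5 states that a patient takes either empagliflozin or placebo in each crossover period. Section 6.6.1 expects one endpoint value per double-blind period.

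**The concern.** A scatter plot of one treatment against the other needs two values per patient, one on each treatment. ANCOVA1 is a between-patient comparison: in period 1 some patients have an empagliflozin value, the others have a placebo value, and nobody has both. Taken at its word, the section orders a figure without patient points.

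Two things might be at stake. First, someone determined to deliver the listed output could fill the missing axis with period 2 values. The display would then mix in the data that the analysis is designed to leave out. Second, a plot of week-4 GFR against baseline by treatment would show the relation that ANCOVA1 assumes (linear, with the same slope under both treatments), and Section 7.4.2.4 does not ask for that plot or for residual diagnostics.

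**Working it through.** The plan states no figure here to reproduce, so the check is a count of the points that each display can show.

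**Inputs**
- Patients randomised and treated: 31 (Section 3). FAS: n = 31 (Section 4, primary endpoint analysis).
- Treatments per patient in one crossover period: 1 (Section 5).
- Endpoint values per patient in one period: 1 (Section 6.6.1).
- Patients without a period 1 value are "excluded from any analysis which only uses data from the first double-blind treatment period" (Section 6.6.1), so 31 is an upper limit for ANCOVA1.

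**Treatment-against-treatment scatter plot (Section 7.4.2.1.3)**

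Points = patients with a week-4 GFR on both treatments within the data used.
- Both periods (MMRM1, and MMRM3 on the log scale): at most 31.
- Period 1 only (ANCOVA1): each patient has one treatment and one value, so 0 of at most 31.

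The 45-degree line and the mean of the two treatments could still be drawn in period 1, because each treatment has a period 1 mean. That mean point would combine two different groups of patients and would say nothing about within-patient differences.

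**Boxplot (Section 7.4.2.1.3)**

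It needs one value per patient, grouped by treatment. Period 1 supplies at most 31 values, so it can be drawn as ordered.

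**Baseline scatter plot (Section 7.4.2.1.4) limited to period 1**

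It needs a baseline value and one week-4 value per patient. Period 1 supplies at most 31 points.

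**Does the text allow period 2 values into the figure?**

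Filling both axes would take 31 × 2 = 62 values, of which 31 (31/62 = 50%) would come from period 2. Section 7.4.2.4 rules this out twice. The data sentence confines the analysis to period 1, and the figure sentence gives its own purpose as examining the effect within period one. The two sentences agree on which data are used. The clash is between Section 7.4.2.4 and the definition it borrows.

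**Is the baseline relation otherwise unexamined?**
- Section 4 makes a general commitment: "The assumptions behind the models will be investigated by way of model diagnostics".
- Section 7.4.2.1.1 defines the diagnostics as a standard look at studentised residuals. A raw scatter plot would not supply these.
- Section 7.4.2.2 (MMRM2) estimates how the treatment effect changes with randomisation baseline GFR, with a confidence interval, and orders "The same set of limited model diagnostics as in" Section 7.4.2.1.1.
- Section 7.4.2.1.4 already orders the baseline scatter plot by treatment.

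The common-slope question is therefore addressed with both periods, which carry more information than period 1 alone.

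**What changes in the results?**

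The ANCOVA1 response, covariate, treatment term and analysis set do not depend on the figure. The estimate, confidence interval and p-value are the same whether the scatter plot is left out, replaced or left as a bare pair of axes.

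**The case for a change.** The best argument for a correction is that the plan orders something impossible and names it. The parenthesis lists the scatter plot explicitly, so the sentence cannot be read as asking for the boxplot alone, and nothing elsewhere in the SAP redefines the plot for period 1. A programmer must then depart from the SAP in some way, and one way, borrowing period 2 values, would defeat the purpose of the section. The correction is also nearly free: one cross-reference and an existing plot program with a period filter.

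The first part stands: the figure cannot be drawn as defined. The rest carries less weight. Borrowing period 2 values would break the section's own restriction, so it is not a reading of the text. The remaining choices, leaving the scatter plot out or drawing week-4 GFR against baseline for period 1, are both harmless.

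Nor does the SAP say that the Section 7.4.2.1.4 plot was the one intended. It is a reasonable guess, because its x-axis is baseline GFR and ANCOVA1 adjusts for randomisation baseline GFR. But the stated aim in Section 7.4.2.4 is to look at the treatment effect, and the boxplot alone serves that aim. The low cost of an edit does not give it a benefit.

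**Conclusion.** The mismatch is genuine and clerical. A sentence that fits the two-period models was carried over to the one-period model, where half of what it orders cannot be drawn. The size is 0 patient points of at most 31 in one descriptive figure; the companion boxplot is unaffected.

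No change to the plan follows. The failure is obvious as soon as the figure is attempted, the sensible responses are all acceptable, and no estimate, interval, p-value or conclusion depends on it. ANCOVA1 is itself a supplementary analysis in a trial that Section 4 says can no longer test its null hypothesis.

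This rests on each patient having one treatment label in period 1, as the as-randomised rule in Section 6.1 implies, and on the figure being kept to period 1 data, as Section 7.4.2.4 requires. The upper limit of 31 assumes that every FAS patient has a period 1 value; fewer would not alter the conclusion.

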## **7.5 SECONDARY ENDPOINT**

### **7.5.1 Key secondary endpoint**

This section is not applicable as no key secondary endpoint has been specified in the protocol.

### **7.5.2 Secondary endpoint**

The secondary endpoint is filtration status ( $\text{GFR} < 120 \text{ mL/min/1.73m}^2$ ) after 4 weeks of double-blind treatment with either empagliflozin or placebo.

#### **7.5.2.1 Primary analysis of the secondary endpoint**

The protocol planned primary analysis of the secondary endpoint in this early terminated trial cannot be performed, because data are too sparse in the predefined subgroup of hyperfilterers.

#### **7.5.2.2 Sensitivity analysis, subgroup analysis, exploratory analysis of the secondary endpoint**

The secondary endpoint will be analysed on all patients in the FAS, only. This was a predefined secondary analysis of the secondary endpoint according to the protocol. No further sensitivity or subgroup analyses are planned for this endpoint.

The endpoint will be analysed using McNemar's test, as well as the odds ratio, 95 % CI and nominal p-value. A table will be presented showing the number of concordant and discordant pairs with each filtration status ( $<120, \geq 120$ ), by treatment. The number of patients omitted due to a missing value will be separately recorded. Descriptive statistics showing the concordant and discordant pairs will also be produced by the filtration status ( $<120, \geq 120$ ), at randomisation baseline and treatment.

The proportion of patients with each filtration status by both treatment and period will be summarised descriptively.

## **7.7 EXTENT OF EXPOSURE**

A descriptive statistics table with mean, SD, median and range of the number of days a patient was on open-label ramipril run-in treatment will be provided for the RIS. The tables will also provide the sum of the total time (in years) that all patients pooled together were on open-label ramipril run-in treatment, as well as descriptive statistics for the mean, minimum and maximum total daily ramipril dose for each patient during the run-in period.

Similar tables will be produced for exposure to ramipril across the whole trial for the RIS.

A descriptive statistics table with mean, SD, median and range of the number of days a patient was on double-blind treatment will be provided for the TS, by treatment. The tables will also provide the sum of the total time (in years) that all patients pooled together were on each double-blind treatment.

A separate listing will be created of any patients that switched treatment at any time during double-blind treatment.

In the above summary tables, the number and percent of patients belonging to each categorical range of exposure weeks will also be provided using the following cumulative categories:

≥ 1 day, ≥ 1 week, ≥ 2 weeks, ≥ 3 weeks, ≥ 4 weeks (for open-label ramipril and double-blind treatment)

≥ 1 day, ≥ 1 week, ≥ 2 weeks, ≥ 3 weeks, ≥ 4 weeks, ≥ 8 weeks, ≥ 12 weeks, ≥ 16 weeks (for total trial ramipril exposure).

Descriptive statistics for the total daily ramipril dose at the start of each double-blind treatment period will be provided for the TS, by treatment. The number and percent of patients who received a total daily ramipril dose less than 10 mg for at least one day during double-blind treatment (excluding washout period) will also be summarised by treatment.

## **7.8 SAFETY ANALYSIS**

Unless otherwise specified below, all safety analysis specified will be performed separately for the open-label ramipril run-in period (on the RIS) and the double-blind treatment period (on the TS).

### **7.8.1 Adverse events**

AEs will be coded using the latest version of the MedDRA coding dictionary at database lock.

Any clinically significant new finding in the physical examination, vital signs (pulse symptoms) and in the 12-lead ECG starting after visit 4 (start of open-label ramipril run-in) will be considered as an AE and will be reported as such.

Unless otherwise specified, the analyses of adverse events will be descriptive in nature and analyses of AEs will be based on the number of patients with AEs (not the number of AEs).

For analysis of AE attributes such as duration, severity, etc. multiple AE occurrence data on the CRF, will be collapsed into AE episodes provided that all of the following applies:

- The same MedDRA lowest level term was reported for the occurrences.
- The occurrences were time-overlapping or time-adjacent (time-adjacency of 2 occurrences is given if the second occurrence started on the same day or on the day after the end of the first occurrence). Exceptions may apply:
  - Genital infection events will not be collapsed if they are representative of different types (i.e. fungal balanitis or vulvovaginitis versus other than fungal balanitis or vulvovaginitis);
  - Sepsis events will not be collapsed if they are representative of different sources of infection (i.e. urinary tract (urosepsis) versus other than urinary tract);
  - Severe hypoglycaemia endpoint confirmed by adjudication will not be collapsed;
  - Hypoglycemia adverse events will not be collapsed (except in case of occurrences with identical onset date, time and glucose value).
- Treatment did not change between the onset of the occurrences OR treatment changed between the onset of the occurrences, but no deterioration was observed for the later occurrence.

For further details on summarization of AE data, please refer to (5).

#### 7.8.1.1 Assignment of AEs to treatment

The analysis of adverse events will be based on the concept of treatment emergent adverse events. To this end, all AEs occurring on or within the respective treatment period will be considered ‘treatment-emergent’. For adverse events, the REP is defined as 7 days after the last dose of treatment (see [Table 6.7: 1](#)).

Owing to the trial design consisting of an open-label ramipril run-in period and the double-blind crossover periods, where periods are defined in [Table 6.1: 1](#), adverse events will be determined as treatment-emergent according to the following rules:

- For the AE summaries of the open-label ramipril run-in period, adverse events will be considered “on-treatment” if they lie on or within the run-in period, as defined in [Table 6.1: 1](#).
- For the AE summaries of the double-blind treatment period, adverse events will be considered “on-treatment” or ‘treatment emergent’ if they lie on or within on-treatment period 1 or on-treatment period 2, as defined in [Table 6.1: 1](#).

AEs occurring on or within the screening period will be referred to as “screening AEs”.

AEs occurring during the treatment x washout period will be assigned to “Treatment x washout”.

AEs occurring on or within the treatment x post treatment period will be assigned to “Treatment x post-treatment”.

AEs occurring on or within the post study period will be assigned to ‘Post study’.

AEs occurring on or within the ramipril post treatment period will be assigned to ‘ramipril post treatment’.

Section 15 summaries of treatment-emergent AEs in the open-label ramipril run-in period will be presented for the RIS.

Section 15 summaries of treatment-emergent AEs in the double-blind treatment period will be presented for the TS, by treatment.

Additional summaries of AEs including off-treatment study periods will be included in Appendix 16.1.9.2.

#### Malignancy and bone fracture events

For malignancy (and respectively bone fracture), in addition to the standard ‘7-day-on-treatment approach’ detailed above, all malignancy (respectively bone fracture) adverse events that occurred between first study drug intake up to study end will be pooled and analysed together in Section 15.

##### 7.8.1.2 Analysis of other significant AEs

Other significant AEs will be reported and summarised according to the ICH E3 criterion. Thus, AEs classified as 'other significant' will include those non-serious and non-significant adverse events with:

- ‘action taken = discontinuation’ or ‘action taken = reduced’, or
- marked haematological and other lab abnormalities or lead to significant concomitant therapy as identified by the Clinical Monitor/Investigator at a Medical Quality Review meeting or Blinded Report Planning Meeting.

##### 7.8.1.3 AE summaries

An overall summary of adverse events will be presented for both the open-label ramipril run-in period and the double-blind treatment period.

The frequency of patients with adverse events will be summarised by treatment, primary system organ class and preferred term. AEs will also be reported by intensity. Separate tables will be provided for patients with other significant adverse events according to ICH E3, for patients with adverse events of special interest (AESI), for patients with serious adverse events, for patients with AEs leading to discontinuation, and for patients with drug-related AEs.

The system organ classes will be sorted according to the standard sort order specified by EMA; preferred terms will be sorted by frequency (within system organ class).

Appendix 16.1.9.2 will also include an analysis on the frequency of patients with non-serious adverse events occurring with incidence in preferred term greater than 5 % by double-blind treatment, for disclosure on clinicaltrials.gov website.

#### 7.8.1.4 AEs of special interest

The protocol defines the following adverse events that for analysis purposes will be considered as AESIs:

- Decreased renal function: creatinine shows a  $\geq 2$  fold increase from baseline and is above the upper limit of normal (ULN)
- Hepatic injury defined by the following alterations of liver parameters after randomization:
  - An elevation of AST and/or ALT  $\geq 3$  fold ULN combined with an elevation of total bilirubin  $\geq 2 \times$  ULN measured in the same blood sample
  - An isolated elevation of AST and /or ALT  $\geq 5$  fold ULN irrespective of any bilirubin elevation.
- Diabetic ketoacidosis (DKA)
- Severe hypoglycaemic episodes

For further details on the definition of DKA and severe hypoglycaemic episodes, refer to Section 5.3.6.1 of the CTP.

Events of these AESIs are identified through the AE being flagged by the investigator as an AESI on the case report form (CRF).

The AESI ‘Decreased renal function’ will be identified by the narrow SMQ “Acute renal failure: 20000003”.

This display will be replicated for present serious events and then events leading to discontinuation.

Acute renal kidney injury will also be discussed based on the creatinine laboratory data increase as detailed in [Section 7.8.2](#).

The AESI ‘Hepatic injury’ will be identified by the narrow SMQs:

- Liver related investigations, signs and symptoms: 20000008
- Cholestasis and jaundice of hepatic origin: 20000009
- Hepatitis, non-infectious: 20000010
- Hepatic failure, fibrosis and cirrhosis and other liver damage-related conditions: 20000013

This display will be replicated for present serious events and then events leading to discontinuation.

Further laboratory analyses will support the hepatic evaluation. See [Section 7.8.2](#) for further details on elevated liver enzyme analyses.

The AESI ‘Diabetic ketoacidosis (DKA)’ will be identified by using both the CEC confirmed ketoacidosis events and the investigator defined Ketoacidosis events.

A frequency table will first summarize the results of the CEC adjudication committee for ketoacidosis events (refer to [Section 7.8.1.6](#) for further details on the adjudication process).

This summary will present the number of patients with CEC:

- certain ketoacidosis
- potential ketoacidosis
- unlikely ketoacidosis
- unlikely ketoacidosis but ketosis
- unclassifiable events

by worst severity and requirement of hospitalisation.

A second frequency analysis will be created and will display the characteristics of ketoacidosis for patients with CEC certain ketoacidosis. These characteristics will include outcome, severity of the worst episode, time to onset of first episode, and lowest blood pH. This analysis will be successively repeated for ketoacidosis endpoints considered by the CEC as potential, as well as for ketoacidosis endpoints considered by the CEC as certain or potential.

Additional analyses will be produced to assess the risk of ketosis. In particular the number of patients with any ketosis events (i.e. CEC confirmed unlikely ketoacidosis but ketosis, and ketosis events derived from the database that were not trigger events for the adjudication) will be summarised.

Other ketoacidosis endpoints as identified by the investigator will be analysed as above.

Frequency of patients with investigator defined AESI ketoacidosis will in addition be tabulated by SOC and PT, as well as using specified trigger search terms for DKA.

The analysis based on specified trigger search terms for DKA will also be restricted to CEC certain ketoacidosis, and to CEC potential ketoacidosis.

Two additional analyses will then be performed to distinguish patients with events based on trigger terms indicative of ketoacidosis and or diabetic ketoacidosis, from patients with events based on trigger terms indicative of acetoaemia.

Serious ketoacidosis will be summarised based on specified trigger search terms for DKA, as well as ketoacidosis leading to treatment discontinuation.

An overview table will first summarize the results of the CEC adjudication committee on ketoacidosis episodes by worst severity.

The CEC certain ketoacidosis episodes will be tabulated by treatment and characteristics of ketoacidosis (e.g. outcome, severity, pre-existing factors, blood pH).

The adjudication outcome results on the ketoacidosis episodes will also be summarised based on how the episode has been identified for adjudication.

Finally, the number of ketosis episodes will be summarised.

The investigator defined AESI ketoacidosis episodes will be summarised by event characteristics, as done on patient level.

The AESI ‘Severe hypoglycaemic episodes’ will be determined by using severe hypoglycaemia AEs reported by the investigator as AESI or severe hypoglycemia that has been confirmed by the adjudication committee.

Refer to [Section 9.3](#) for further details on the derivation of the severe hypoglycaemia adverse event endpoints analysed in this section.

For the analysis of number of patients with severe hypoglycaemia adverse event, a frequency table will first summarize the results of the adjudication committee on hypoglycaemic events that had been sent to the CEC for adjudication.

Patients with CEC confirmed severe hypoglycaemia will be tabulated by treatment and characteristics of hypoglycaemia including minimum glucose level and time to onset of first episode. The frequency of severe nocturnal hypoglycaemia AE (i.e. any hypoglycaemia event with an onset from 0:00 midnight to 5:59 a.m.) will also be evaluated as part of these characteristics.

Patients with investigator defined AESI severe hypoglycaemia will also be summarised by treatment and event characteristics.

Patients with investigator defined AESI severe hypoglycaemia will be then summarised by SOC, PT and treatment group.

Finally, severe hypoglycaemia considered serious or requiring third person assistance will be tabulated using the narrow SMQ Hypoglycaemia. This analysis will be repeated for patients with CEC confirmed severe hypoglycaemia.

For the analysis of frequency of hypoglycaemic adverse events, the number of CEC confirmed severe hypoglycaemic episodes will be first tabulated by treatment and characteristics of hypoglycaemia.

In addition, the severe hypoglycaemic episodes that have been confirmed by the adjudication committee will be represented on a graph by hour of the day (from midnight to 11:59 pm).

The investigator defined AESI severe hypoglycaemic episodes will finally be summarised by event characteristics, as done on patient level.

